4.3. Treatment Compliance

For each subject, the treatment compliance rate is estimated as follows

$$\text{Compliance rate (\%)} = \frac{100 * \text{Number of days of taking study drug}}{\text{Total treatment duration in days (excluding intended treatment interruptions)}}$$

where the number of days taking study drug is defined as the total treatment duration (from the first dose to the last dose) excluding all interruptions regardless of intentional or not.

Adherence to study regimen for an individual subject is considered acceptable in this study if the compliance rate is 75% or higher.

For the purpose of compliance rate calculation, interruptions due to AE, outcome events, bleeding events, prohibited medication, or surgical/invasive procedures are considered intentional interruptions. Interruptions due to other reasons are considered non-intentional. Missing doses during intentional interruption periods will not be counted in the compliance rate calculation. If the dose date prior to a treatment interruption is missing, the same imputation rule for imputing the last dose date described in [Section 2.1](#) will be used to impute the dose date.

The median, the inter-quartile range, and the range of compliance rate will be summarized by treatment. In addition, if information is sufficient, the compliance rate in each treatment group will be depicted by a cumulative distribution function (CDF).

The proportion of subjects with acceptable treatment adherence as defined above will be provided.

4.4. Extent of Exposure

Subject level duration of treatment exposure is defined as the duration between the first dose day and last dose day. Note that temporary study drug interruptions are included in this definition.

The mean, standard deviation, median, the inter-quartile range, and the range of duration of treatment exposure will be summarized by treatment. In addition, the duration in each treatment group will be depicted by a CDF.

The duration will also be summarized by the following categories:

- ≤ 90 days
- 91 – 180 days
- 181 – 360 days
- 361 - 540 days
- 541 – 720 days
- 721 - 900 days
- 901 – 1080 days
- 1081 – 1260 days
- > 1260 days

4.5. Protocol Deviations

Major protocol deviations will be summarized by treatment group for the all randomized data set. The categories of protocol deviations will include the following:

- Entered but did not satisfy criteria
- Received a disallowed concomitant treatment ([Attachment 3](#))
- Received wrong treatment or incorrect dose (includes subjects with treatment compliance rate $< 75\%$ calculated according to a formula described in [Section 4.3](#))
- Developed withdrawal criteria but not withdrawn
- Other (as appropriate)

4.6. Prior and Concomitant Medications

This study collects limited prior and/or concomitant medications, such as medications related to subject's HF and CAD. Medication will be classified using the Anatomical Therapeutic Chemical (ATC) classification system in WHO drug dictionary. The prevalence of medication use by ATC term will be summarized by treatment group and by study phase (prior to randomization, during the study drug therapy period, and after last dose of study drug [post-treatment]). A medication prior to randomization is considered as a prior medication. A medication with a use period overlapping with the study drug therapy period is considered as a concomitant medication. A medication that starts after the day of the last dose of study drug is considered as a post-treatment medication. Note that a medication can be categorized into multiple study phases if its use spans more than one study phase. In such a case, the medication use will be included in more than one summary.

5. EFFICACY

5.1. Analysis Specifications

Only outcome events with adequate supporting documentation as specified in the protocol will be included in the main analyses described below. All events reported by investigators, regardless of adequacy of supporting documentation, will only be included as part of sensitivity analyses. The adequacy of documentation will be determined prior to data unblinding.

If it is determined prior to data unblinding that fraud or misconduct occurred at a clinical study site during the conduct of the study, all subjects at that site will be excluded from primary efficacy analysis. Other findings of noncompliance with Good Clinical Practices (GCP) will be assessed to determine whether subjects affected will need to be removed from analyses. Subjects to be excluded from analyses due to fraud or misconduct of a clinical study site will be documented prior to data unblinding.

5.1.1. Level of Significance

The family-wise type I error rate for the primary efficacy endpoint will be controlled at the 5% level (2-sided). This is achieved by using the Lan-DeMets α spending function approach. If superiority is established for the primary efficacy endpoint, secondary endpoints will be tested in a fixed sequence, each at a significance level corresponding to the Pocock-type boundary. If an individual test during any step is not statistically significant, further treatment comparison may continue (i.e., reporting of p-values) but significance will not be claimed.

Confidence intervals (CIs) are calculated at the 95% nominal confidence level. In addition, repeated CI (RCI), which adjusts for the interim analysis, will also be provided in the Clinical Study Report (CSR).

5.1.2. Data Handling Rules

If the date of an outcome event is missing or partially missing, the date at the middle of the logically possible range will be imputed as the event date. If there is a tie between 2 such dates, (i.e., the number of days within the possible range is an even number), the later date will be used.

In the case that it cannot be determined if an event occurs before or after randomization, the event is always considered as a post-randomization event and the randomization date is used as the start of the logically possible range. On the other hand, in the case that it cannot be determined if an event occurs before or after GTED, the occurrence date is always considered not later than the GTED. In this case the GTED is the end of the logically possible range.

5.2. Primary Efficacy Endpoint(s)

5.2.1. Definition

The primary efficacy endpoint is the time from randomization to the first occurrence of ACM, MI, or stroke. Subjects who do not have any of these outcome events will be censored at the end of the analysis observation period as defined in Section 2.3.1.

5.2.2. Analysis Methods

The primary statistical null hypothesis is that there is no difference between treatment groups in distribution of the time from randomization to the first occurrence of ACM, MI, or stroke, and the alternative hypothesis is that there is a difference in the distribution between treatment groups.

The primary statistical hypothesis will be tested using a log-rank test, stratified by region. The primary analysis will be based on the analysis set defined by ITT subject population and the up-to-GTED observation period (up to the cut-off date to be specified for the interim analysis, see details below). Subjects will be analyzed according to the treatment group to which they are randomized, irrespective of actual treatment received. The overall α level is 5%, 2-sided. In addition to the final analysis, the primary statistical hypothesis will be tested in an interim analysis when primary efficacy events are observed in approximately 600 unique subjects. A Lan-DeMets α spending function with O'Brien-Fleming type of boundaries will be used to preserve the overall type I error rate. If the log-rank test statistic crosses the stopping boundaries, and the log-rank statistic is less than 0, (i.e., the observed number of events in the rivaroxaban group is less than the expected number of events under the null hypothesis), it will be concluded that the study has demonstrated that rivaroxaban is superior to placebo in reducing the risk of the composite of ACM, MI, and stroke in the population studied.

It is expected that risk of death will be the highest immediately following the index event or following subsequent episodes of re-hospitalization for heart failure. Therefore, the cumulative event rate derived from the Kaplan-Meier estimate will be displayed graphically to evaluate the timing of event occurrence and the consistency of the treatment effect over time.

The magnitude of the RRR will be estimated using a Cox proportional hazards model, stratified by region, with treatment (as randomized by IWRS) as the only covariate. The point estimate and corresponding 95% CI, which will be calculated using 95% as the nominal significance level, for the hazard ratio (rivaroxaban to placebo) will be reported. In addition, a RCI will be calculated based on the procedure described in Jennison and Turnbull (2000), where significance level at the interim analysis and the final analysis will be approximately 99.7% and 95.2%, respectively. The plausibility of the proportional hazards assumption will be assessed by visually comparing

the plot of the log of the cumulative hazard function between treatments, and formally tested by adding a treatment by logarithm-transformed time interaction into the Cox model. A p-value greater than 0.05 for the interaction term will be interpreted as no statistical evidence against the proportional hazard assumption. If the p-value is 0.05 or less, post-hoc analyses will be conducted to estimate the magnitude of treatment effect by time. These post-hoc analyses include, but are not limited to, adding a function of time, such as time interval indicators, by treatment interaction as covariates to the Cox model. Treatment effects for different time intervals, such as < 12 months versus > 12 months, etc., will be reported as appropriate.

Sensitivity analyses will also be conducted to assess the robustness of the primary efficacy analysis. These include, but are not limited to, a log-rank test stratified by country and an un-stratified log-rank test, repeating analyses mentioned above for the analysis set defined by the up-to-GTED observation period and the ITT subject population; for the analysis set defined by the on-treatment observation period and the per-protocol subject population; for the analysis set defined on-treatment observation period and the safety subject population; and for the analysis set defined by the post-randomization observation period and ITT subject population. The primary efficacy endpoint will also be analyzed for the ITT subjects who enrolled under the original protocol and who enrolled under the amended protocols for the Up-to-GTED observation period.

The percentage of events reported by investigators with adequate protocol-specified documentation will be reported.

The RRR for the components of the primary efficacy endpoint will be evaluated using a Cox proportional hazards model as described above.

Extensive efforts will be made to collect complete data for all subjects randomized in this study. Subjects will be followed up to the end of the study, and all required data will be collected, regardless of subjects' compliance with study drug regimen or visit schedule. For subjects who are lost to follow up or who withdraw consent, efforts will be made to obtain their vital status at the end of study from permitted sources.

Although extensive effort will be made to reduce the number of subjects with missing follow-up, it is expected that there will be missing vital status and event information in some subjects. Sensitivity analyses will be performed to evaluate the potential impact of missing data on analysis results and robustness of study conclusions. Distributions of baseline demographics and other characteristics will be compared between subjects who complete the study and subjects who do not complete the study, accounting for treatment and regardless of treatment, to evaluate the plausibility of the non-informative assumption used in the analysis. In addition, reasons of early discontinuation from the study will be summarized by treatment group.

The potential impact of missing data on the primary efficacy analysis will be evaluated by imputation, where events will be imputed in missing follow-up periods. The imputation will be done based on various assumptions for unobservable event rates in missing follow-up periods, which may depend on treatment groups and/or reasons of early discontinuation. Additional

details of these sensitivity analyses, including specifications for imputation, will be provided in a separate document that will be finalized prior to the database lock.

Homogeneity of treatment effects, both in the magnitude and direction of RRR, across subgroups will be assessed by subgroup analyses. Subgroups to be included in the subgroup analyses are defined in Section 2.4.

Interactions between treatment and baseline covariates with continuous values, such as age and D-dimer, will also be evaluated on a continuous scale in addition to categorical scales.

For subgroups specified in Section 2.4, annualized event rates will be provided by treatment and by subgroup. If there are at least 10 events in each of the cells defined by combinations of treatment and subgroup, statistical testing will be done to test the homogeneity of the treatment effect hypothesis. Statistical testing will be conducted for each set of subgroups individually, by adding covariate(s) for the subgroup and the corresponding treatment-by-subgroup interaction in the Cox proportional hazards model specified above, one at a time, except for the assessment of a region effect. An un-stratified Cox model will be used when assessing the homogeneity of treatment effect across regions. For subgroups with natural ordering, such as subgroups defined by eGFR, Body Mass Index, and NYHA classification, an ordinal covariate will be created to indicate subgroups. If a non-monotonic trend is observed, additional subgroup analyses based on non-ordinal categories may be further explored. For other subgroups without natural ordering, such as subgroups defined by race or region, a set of indicator covariates will be created to indicate subgroups. If the p-value for the interaction is greater than 0.05, the test result will be interpreted as a lack of statistical evidence for a difference in the treatment effect between the subgroups. Otherwise, a Gail-Simon test will be performed to assess if the interaction is also qualitative. If the p-value from the Gail-Simon test is greater than 0.05, the result will be interpreted as a difference in the size of treatment effect between the subgroups with a lack of statistical evidence for the difference in the direction of treatment effect (i.e., only quantitative but not qualitative interaction). If the p-value is less than or equal to 0.05, it will be interpreted as a directional difference in treatment effect between subgroups (i.e., qualitative interaction). Given the large number of subgroup analyses explored without multiplicity adjustment, observing p-values less than 0.05 due to chance alone is expected. Therefore, results of the subgroup analyses will be interpreted with caution.

The above univariate subgroup analyses will be supplemented by a multivariate analysis, which will assess the effects of baseline demographics and disease characteristics collectively using an un-stratified Cox proportional hazards model that contains main effects of treatment and subgroups, and interactions between treatment and subgroup (2-way interactions only). This approach adjusts for correlations between variables and evaluates the net effects of subgroups. A backward selection procedure will be employed. In the backward selection procedure, the variable with the largest p-value will be eliminated from the model one at a time. A main effect cannot be removed from the model before the corresponding interaction with treatment is removed. The backward selection procedure ends when no more covariates can be removed from the model with the exit p-value threshold of 0.05.

5.3. Secondary Efficacy Endpoints

5.3.1. Definition

There are 4 secondary efficacy endpoints specified in this study:

- Time to the first occurrence of CV death or re-hospitalization for worsening of HF
- Time to CV death
- Time to re-hospitalization for worsening of HF
- Time to re-hospitalization for CV events

5.3.2. Analysis Methods

If superiority of rivaroxaban over placebo with respect to the primary efficacy endpoint is established, the secondary endpoints will be tested in the sequence specified above. The determination of the order is based on clinical relevance and power consideration. Each secondary endpoint will be tested using the same analysis methods that are described for the primary efficacy endpoint. The significance level of each individual test corresponds to the Pocock-type boundary, irrespective of whether the study is completed as planned or stopped early at the interim analysis. If p-value for a hypothesis is greater than that significance level, all remaining hypotheses after this hypothesis in the fixed sequence will not be rejected.

A supporting analysis of time to the first occurrence of ACM or re-hospitalization for worsening of HF will also be performed using the same analysis method as for the primary efficacy endpoint.

As supplemental analyses, the effect size of rivaroxaban versus placebo in terms of re-hospitalization for worsening of HF and for CV events will also be estimated using parametric, semi-parametric, and non-parametric approaches. In contrast to time to the first occurrence used in the analyses mentioned above, all occurrences will be included in these supplemental analyses. A parametric frailty model will be used in the parametric approach. The frailty model assumes that events follow a renewal process with a time-independent hazard that varies from subject to subject, and the distribution of the subject-dependent hazard follows a Gamma distribution, which is treatment specific. The resulting analysis is a generalized linear regression model based on negative binomial distribution, where the covariates are duration of risk exposure, treatment, and the interaction between them. The semi-parametric approach is the Andersen-Gill model ([Andersen and Gill, 1982](#)) with a robust estimate for variance that takes intra-subject correlation into account ([Lin and Wei, 1989](#)). The non-parametric analysis is based on the unmatched win-ratio method proposed by [Pocock et al \(2012\)](#).

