1. INTRODUCTION

This statistical analysis plan (SAP) specifies definitions of analysis sets, key derived variables and statistical methods for analysis of efficacy and safety for the Phase 3 study RIVAROXAHF3001 (also known as COMMANDER HF). This SAP is based on the Clinical Protocol RIVAROXAHF3001, originally finalized on April 18, 2013 and all its amendments.

Titles, mock-ups and programming instructions for all statistical outputs (tables, figures and listings) are provided in a separate document entitled Data Presentation Specifications (DPS).

An Independent Data Monitoring Committee (IDMC) will monitor safety during this study, review interim efficacy and safety results, and make a recommendation whether the study will be continued as planned, or terminated early for overwhelming superiority, futility, or safety. Safety data will be reviewed by the IDMC periodically and additional details for the planned interim analysis are specified in the abbreviated IDMC SAP, which was specifically prepared for IDMC use.

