1.4. Sample Size Justification

This is an event driven study. The study was designed to observe occurrences of the primary efficacy event in 984 unique randomized subjects, on or before the GTED, to have 90% power to detect a 20% relative risk reduction (RRR, defined as one minus hazard ratio) in the composite of ACM, MI, or stroke at 5%, 2-sided significance level. A total of approximately 5000 subjects will be randomly assigned to either the rivaroxaban arm or the placebo arm in a 1:1 ratio.

The above sample size calculation was estimated based on the following additional assumptions:

- Event rate for the composite endpoint in the placebo arm: 19%/year
- Permanent premature treatment discontinuation rate: 10%/year
- Lost-to-follow-up: 1%/year
- Duration of enrollment period: 24 months (see [Attachment 1](#) for distribution of enrollment by month)
- Duration of study (from first subject randomized to last EOS visit): 31 months

The assumptions of RRR and event rate were based on observations from HF subjects in the ATLAS ACS 2 TIMI 51 study. Observed data from HF subjects of ATLAS ACS 2 TIMI 51 study are summarized in the table below (Source: Adhoc analyses on file).

	Event Rate (%/patient-year)		Hazard Ratio (95% CI)
	Rivaroxaban 2.5 mg bid	Placebo	
HF Subjects	(N=562)	(N=558)	
ACM/MI/Stroke	9.43	16.64	0.57 (0.41, 0.79)
ACM	3.54	8.31	0.43 (0.26, 0.70)
MI	5.73	8.47	0.67 (0.44, 1.03)
Stroke	1.08	1.60	0.69 (0.26, 1.81)

Based on historical data, the mortality rate in this study was expected to be higher, and the rate of MI was expected to be lower, than the observed corresponding rates in ATLAS ACS 2 TIMI 51 study. After adjusting for differences in these event rates, an event rate of 19%/year for the composite endpoint in the placebo group was used in the sample size calculation. Event rates in the placebo group for the components ACM, MI, and stroke are expected to be approximately 14%, 4%, and 2% per year, respectively.

Although the RRR observed in ATLAS ACS 2 TIMI 51 study was 43% (95% CI [21%, 59%]), a RRR of 20% was assumed in the sample size calculation. The lower RRR close to the lower bound of the 95% CI was used to be conservative because the subject population in the current study was considered different from the HF subgroup in ATLAS ACS 2 TIMI 51.

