The study is revised to observe occurrences of the primary efficacy event in 1,200 unique randomized subjects based on a simulation study performed on available trial data, i.e., longer enrollment period, lower than anticipated primary efficacy event rate, higher than anticipated study drug discontinuation rate:

- Event rate in the placebo arm: approximately 16%/year based on the observed combined event rate at 14%/year (assumed 20% of RRR remains)
- Early permanent study drug discontinuation rate: approximately 13%/year
- Duration of enrollment period: approximately 48 months (projected)

The simulation study estimated that the duration of study may extend to approximately 54 months based on the fact that the original goal of enrolling a total of 5,000 subjects remains

unchanged and all subjects would be observed for approximately 6 months after the last subject is enrolled.

With an effect size of 20% and overall α level of 5% (2-sided), 1,200 primary efficacy events will produce a statistical power of approximately 80%.

An interim analysis will be conducted when primary efficacy events are observed in approximately 600 unique subjects (see Section 3 for more details).

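### The negative binomial model for recurrent re-hospitalizations has more terms than its stated constant-hazard process yields, so its treatment coefficient would not be the overall rate ratio (minor)

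*SAP*

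**What the plan says.** Section 5.3.2 places this model outside the tested sequence. The sentence that opens with "As supplemental analyses, the effect size of rivaroxaban versus placebo in terms of re-hospitalization for worsening of HF and for CV events will also be" goes on to name three approaches, one parametric, one semi-parametric and one non-parametric, and the section counts every re-hospitalization and not only the first.

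The parametric approach is a frailty model in which "events follow a renewal process with a time-independent hazard that varies from subject to subject". On how that hazard varies, the SAP adds this assumption about the arms: "the distribution of the subject-dependent hazard follows a Gamma distribution, which is treatment specific". It then presents a negative binomial regression as what results from these assumptions, "where the covariates are duration of risk exposure, treatment, and the interaction between them".

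It names no link, no offset, no scale or unit for duration, and no follow-up time at which the arms are compared. Section 2.3.1.1 fixes the population and data window for all efficacy endpoints (ITT, up to GTED), but a data window is not a time at which to read a contrast. Section 1.2 expects a double-blind phase of 6 to 54 months, so exposure differs widely between subjects.

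**The concern.** The covariate list is offered as a consequence of the process, but it is not one. A constant hazard whose mean depends on the arm makes expected counts proportional to time in each arm, so the ratio between arms is the same at every follow-up time. A model with duration, treatment and their interaction lets that ratio vary with time. The effect size then depends on the time at which it is read.

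A programmer who takes the list literally under the usual log link, and reports the exponentiated treatment coefficient, would give the ratio at zero follow-up (raw duration) or at one time unit (log duration). Both lie at the edge of the data or outside it. The cost is precision, and with log duration the number would change with the choice of years or months. At stake is the readability of one supplemental estimate.

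**Working it through.** The SAP gives no figure for this model, so there is none to reproduce.

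**Algebra.** Let N be a subject's count, t the time at risk, A = 1 for rivaroxaban, m_P and m_R the arm mean rates, and f a Gamma frailty with mean 1. If N given f is Poisson(f × m × t), then N is negative binomial with E[N] = m × t. The ratio of expected counts is m_R/m_P at every t. A Gamma shape that differs by arm changes the dispersion but not this ratio. With m_P = 0.30 and m_R = 0.24 per year, the ratio is 0.80 at 0.5, 1, 2 and 4.5 years.

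**Does the listed model follow?** Write the mean model as b0 + b1·D + b2·A + b3·A·D, where D is duration on some scale.

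- *Log link, D = t.* The process needs log m + log t, which is not linear in t, so this form does not contain it. The fitted ratio is exp(b2 + b3·t); exp(b2) is the ratio at t = 0.
- *Log link, D = log t.* The process is the case b1 = 1, b3 = 0, b2 = log(m_R/m_P), so the interaction is not needed. The fitted ratio is exp(b2) × t^b3; exp(b2) is the ratio at t = 1 unit. Going from years to months replaces b2 by b2 − b3 × log 12 = b2 − 2.485 × b3, so the coefficient depends on the unit unless b3 is 0.
- *Identity link, D = t.* The process is b0 = b2 = 0, b1 = m_P, b3 = m_R − m_P. Duration and the interaction are both needed; the treatment main effect is surplus.

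**Simulation inputs.** From the SAP: 5,000 subjects, 1:1; loss 1% per year; mortality 14% per year (Section 1.4; 10% assumed in one scenario); observed enrolment summing to 3,099 over 34 months (Attachment 1); enrolment ending at month 48 and study end at month 54 (Section 1.4). Assumed: the remaining 5,000 − 3,099 = 1,901 subjects enrol uniformly over months 34 to 48; placebo rate 0.2 to 0.4 per year; frailty variance 1.5 to 3; true ratio 0.80; death either independent of frailty or linked to it; equal mortality by arm. There were six scenarios of 1,500 trials each, fitted by maximum likelihood with dispersion by arm. Mean follow-up was 1.8 to 1.9 years. Under the offset model the SD of the log ratio was 0.061 to 0.067.

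| Mean model | Read at | SD relative to offset model | Trials more than 10% from own offset estimate |
|---|---|---|---|
| Log link, raw duration | zero (treatment coefficient) | 1.83–2.13 | 31–40% |
| same | 1 year | 1.2–1.5 | not tabulated |
| same | mean follow-up | 0.95–1.07 | none |
| same | 4 years | 1.7–2.1 | not tabulated |
| Log link, log duration, years | 1 year (treatment coefficient) | 1.16–1.62 | 2–21% |
| Log link, log duration, months | 1 month (treatment coefficient) | 4.00–5.73 | 68–78% |
| Log link, log duration | mean follow-up | 0.94–1.01 | none |
| Identity link, duration and interaction only | ratio of slopes | 1.00 | same mean model |
| Identity link, all listed terms | ratio of slopes | 1.40–1.52 (death independent), 2.75–3.13 (linked) | not tabulated |
| Identity link, all listed terms (150 trials each; rate 0.3, variance 2) | mean follow-up | 1.01 (independent), 0.93 (linked) | none; largest gaps 2.9% and 5.6% |

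Average estimates in the six scenarios were 0.78 to 0.81 under every reading.

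**What the SD ratios mean.** Take an offset SD of 0.064, the middle of its range. Around 0.80, 95% of estimates fall within 0.80 × exp(±1.96 × 0.064) = 0.71 to 0.91. At 2 times that SD the range is 0.62 to 1.03; at 5 times, 0.43 to 1.50.

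**Second simulation.** This used different assumptions: potential follow-up uniform over 0.5 to 4.5 years, rate 0.30 per year, Gamma shape 0.5, 30 trials of 5,000. The offset ratio averaged 0.796 (SD 0.050). The log-duration form had SD 0.155 at 0.5 years but 0.053 at 2 years; the identity form had 0.147 and 0.048. In one sample of 200,000, every form gave 0.798 to 0.821 at all times read. The pattern is the same: loss of precision at early reading times, no material bias.

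**The case against.** The strongest reply is that the list is mostly right. On the identity scale the stated process calls for duration and duration by treatment, with the interaction carrying the effect. The treatment term is then merely surplus: it nests the true model and does not contradict it. Treatment might also have been listed because the Gamma is treatment specific and so must enter the dispersion. The first part stands, and it limits the point to the full three-term mean model. The second is possible, but Section 5.3.2 does not say it.

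The large SD ratios arise only if the treatment coefficient, or a ratio of slopes that ignores fitted intercepts, is reported. The SAP prescribes neither. This stands too: at mean follow-up the forms can hardly be told apart.

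The offset is also partly a choice. With death linked to frailty, fitted log-duration slopes were 0.48 to 0.57 and not 1, and the freer log-duration model was slightly more precise (0.94 to 0.96 times the offset SD at mean follow-up). With the linked death hazard also 20% lower on rivaroxaban, slopes differed by arm (0.48 against 0.53; difference 0.047, SE 0.008). The offset estimate still drifted less (0.82 against 0.84, truth 0.80). A reader might infer that the interaction is always redundant. That was shown only for equal mortality by arm.

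A reader might also treat the unstated link and duration scale as an omission in itself. The SAP says that "Titles, mock-ups and programming instructions for all statistical outputs (tables, figures and listings) are provided in a separate document", and that document is not at hand, so these details may stand there. The covariate list and its claimed derivation, however, are in the SAP.

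Finally, a reader might see a conflict with the primary Cox model, which is "stratified by region, with treatment (as randomized by IWRS) as the only covariate". There is none: a Cox model handles follow-up through risk sets and needs no duration term.

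**Conclusion.** The point holds as a minor one. The three-term mean model does not follow from the process from which Section 5.3.2 says it results, and its treatment coefficient under a log link is not the overall rate ratio. If that coefficient were reported, its SD would be about 1.8 to 2.1 times the offset model's with raw duration, 1.2 to 1.6 times with log duration in years, and 4.0 to 5.7 times in months. These figures rest on assumed re-hospitalization rates, frailty variances and late enrolment, because the SAP gives none of them. The algebra does not depend on them.

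A reader might infer that the planned estimate is biased, or that a confirmatory conclusion is at risk. Neither is supported. Average estimates stay near the true value under every reading in the six main scenarios, and at mean follow-up no trial was more than 10% from its own offset estimate. The model is one of three supplemental estimates, beside the Andersen-Gill model and the win ratio, and it enters neither the primary test nor the fixed sequence.

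**What to change.** Replace the covariate list in Section 5.3.2 with: negative binomial regression with log link, log of time at risk as offset and treatment as the only covariate in the mean; dispersion by arm if the Gamma is to be treatment specific; rate ratio with 95% CI reported.

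If duration terms are kept as a check on the constant-hazard assumption, for example because death may be linked to frailty, state the link and the duration scale and unit, and report the contrast at mean follow-up and not the treatment coefficient.

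The cost is one sentence in the SAP and no new data. The offset is a standard option of a negative binomial fit; arm-specific dispersion needs some extra model code. Settling this before unblinding removes a choice among differing effect sizes.
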